- 4 Assessment can be performed prior to visit 10, if CT scan from visit 9 is available.
- 5 For women of childbearing potential only (please refer to sections [3.3.3](#) (exclusion criterion 20) and [5.2.3.1](#))
- 6 For details refer to [section 5.2.3.1](#)
- 7 Screening for tumour lysis syndrome in between safety laboratory assessments ([section 5.2.3.2](#))
- 8 Quantitative CMV DNA PCR ([section 5.2.3.3.2](#))

Proprietary confidential information.

© 2016 Boehringer Ingelheim International GmbH or one or more of its affiliated companies. All rights reserved.

This document may not - in full or in part - be passed on, reproduced, published or otherwise used without prior written permission.

Flowchart for Course 3, End of Treatment visit and Follow-up

Trial Periods	Treatment and observation/rest									EOT	FU
Course *	3										
Week	15	16	17	18	19	20	21	23	25	see 	
Visit **	1	2	3	4	5	6	7	8	9		
Days	1	8	15	22	29 (+2)	36 (+5)	43 (+5)	57 (±5)	71 (±5)		
Eligibility for course 3	x 										
Vital signs 	x	x	x	x	x	x	x	x	x	x	x
Weight	x	x	x	x	x	x	x	x	x	x	x
Physical examination, incl. tumour size (lymph nodes, spleen, liver),	x			x			x			x	x
Disease / response assessment (clinical/imaging)	x			x 						x	x 
Serum pregnancy test 	x			x						x	
Concomitant therapy	x	x	x	x	x	x	x	x	x	x	x 
General safety laboratory parameters 	x	x	x	x	x	x	x	x	x	x	x
Administration of BI 836826	x	x	x	x							
Screening for Tumour Lysis Syndrome 	x	x									
Adverse events	x	x	x	x	x	x	x	x	x	x	x 
CMV monitoring 	x	x	x	x	x	x	x	x	x	x	x
Lymphocyte typing (B/T/NK cells)	x	x	x	x	x	x	x	x		x	x
CT scan of neck, thorax, abdomen and pelvis									x	x 	
12-lead ECG										x	
Completion of active trial treatment										x	
Status (remission, progression, death)										x	x
Other therapy for lymphoma										x	x

EOT: End of treatment visit, to be performed at withdrawal from further treatment (<12 administrations) or at the latest 8 weeks after the last administration of BI 836826 (12 administrations)

FU: Follow-up visits (starts after EOT) at least every 6 weeks until 6 months after EOT visit, details see [section 6.2.3.2](#)

CMV: Cytomegalovirus

\* the planned duration of course 3 is 12 weeks (84 days)

\*\* the visit number follows the course number, i.e. visit 2 course 1 will read C1\_V2 and visit 2 course 2 will read C2\_V2 ...

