1 Can be performed within 7±2 days prior to this visit

2 For details during and after infusion of BI 836826, refer to [section 5.2.5.1](#)

3 Disease / response assessment will be based on clinical judgement when recent CT is not available

4 For women of childbearing potential only (please refer to [sections 3.3.3](#) (exclusion criterion 20) and [5.2.3.1](#))

5 Concomitant therapy during FU only in case indicated for treatment of an AE (section [4.2.1](#))

6 For details refer to section [5.2.3.1](#)

7 Screening for tumour lysis syndrome in between safety laboratory assessments (section [5.2.3.2](#))

8 For AE assessment during FU refer to sections [5.2.1](#) and [6.2.3.2](#)

Proprietary confidential information.

© 2016 Boehringer Ingelheim International GmbH or one or more of its affiliated companies. All rights reserved.

This document may not - in full or in part - be passed on, reproduced, published or otherwise used without prior written permission.

9      Quantitative CMV DNA PCR (section [5.2.3.3.2](#))

11     In case end of treatment occurs before week 26, a CT scan can be performed at the EOT visit if clinically indicated for response assessment (*e.g.* progression)

12     If 12 infusions has been administered the EOT should be performed at the latest in week 26 (day 77±5 of course 3)

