## **5.2.3 Assessment of safety laboratory parameters**

### **5.2.3.1 General safety laboratory parameters**

Blood samples and urine have to be collected at the time points specified in the [flowchart](#). Safety laboratory examinations will include haematology, biochemistry, coagulation and qualitative urine analysis.

Haematology	Haemoglobin, red blood cell count (RBC), white blood cell count (WBC) with differential, platelets (PLT)
	Reticulocytes have to be measured only at visit of the first and last administration of each treatment course, at the EOT visit and during follow-up.
Biochemistry	Glucose, sodium, potassium, calcium, inorganic phosphate, creatinine, aspartate amino transferase (AST), alanine amino transferase (ALT), alkaline phosphatase (AP), lactate dehydrogenase (LDH), total bilirubin (if elevated provide direct bilirubin), urea, total protein, albumin, uric acid
	Serum immunoglobulin levels (IgG, IgM, IgA), direct antiglobulin test have to be measured only at visit of first and last administration of each treatment course, at the EOT visit and during follow-up.
Coagulation	Activated partial thromboplastin time (aPTT), prothrombin time (PT)/international normalised ratio (INR)

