### 6.2.3 End of treatment and follow-up period

#### 6.2.3.1 End of treatment

The end of treatment (EOT) visit should be performed if patient and investigator refrain from further therapy at any time during the treatment period. For patients who receive course 3 (12 administrations) at the latest 8 weeks after the last administration of BI 836826. If the patient concludes the trial within a treatment course, the information required to be collected at the EOT visit should be obtained as early as possible, preferably immediately. This includes a CT scan, which may be performed if it is considered clinically indicated, *e.g.* to document disease progression. At the EOT visit assessment of all safety and efficacy parameters should be performed according to flowchart for course 3. The status of the patient at EOT has to be documented, *e.g.* in case the patient has progressive disease the date of first documentation of PD has to be recorded. The reason for the completion of active trial treatment or premature discontinuation of trial, if applicable, has to be stated together with date of last administration of the trial drug. If the patient receives other therapy for lymphoma, the therapy has to be stated by name and date of first treatment. For detail see [flowchart](#) for Course 3.

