6. GENERAL ANALYSIS DEFINITIONS

6.1 TREATMENTS

In this Phase I trial, treatments are not randomised (open-label, dose escalation). Different dose levels of BI 836826 can arise. The data will be presented for all dose cohorts separately, where Korean patients will be presented as a separate dose cohort from Caucasian patients.

In addition, the results for all patients in total, all Caucasian patients in total, and all Korean patients in total will be presented.

To justify the MTD determination, DLTs occurring during the MTD evaluation period (very first infusion of BI 836826 until the day of second infusion in Course 1 + seven days) will be presented separately from those occurring during the complete on-treatment period.

“Analysing treatment” will be used for reporting of treatment emergent AEs and to differentiate between screening, on-treatment and post-study safety data. The inequalities start date \leq onset date of AE $<$ end date will determine whether the AE will be assigned to the “analysing treatment” or not.

For the on-treatment period and the MTD evaluation period, the initial trial medication assigned at the beginning of the first treatment course will be used as the label of the analysing treatment.

AEs that have an onset date during the screening or post-study periods will be displayed in separate listings from those occurred during the on-treatment period.

The actual planned dose of trial medication administered on the day each AE started will also be derived. This will be presented in patient listings, but will not be used for defining treatments for analysis.

Labels of each analysing treatment period, analysis numbers, the labels used for display in the tables and listings in the CTR, as well as codes, decodes, sort order and labels for each trial medication used in this trial are provided in the TSAP technical document “ADS Plan”.

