7.8.1.2 Adverse events

AE analysis will be performed for all treatment periods and selected analyses for the MTD evaluation period.

The analyses of AEs will be descriptive in nature and will follow the standard procedure laid down in the Data Management and Statistics Manual (DM & SM) (including all required tables and listings) (current guideline 'Handling and Summarization of AE Data for CTR and Integrated Summaries' (6)). AEs will be coded with the most recent version of Medical Dictionary for Regulatory Activities (MedDRA). The version number will be displayed as a footnote in the respective tables and listings. The SOC will be sorted alphabetically, and PTs will be sorted by descending frequency of adverse events in the "Total" BI 836826 group

Each patient can be observed during the trial under several doses. Analysing the AE of all treatment courses will be carried out under the initial treatment. No formal statistical analysis is planned for the safety comparison.

The analysis of AEs will be based on the concept of treatment emergent AEs. That means that all AEs occurring between the first administration of BI 836826 until 8 weeks after last administration of BI 836826 will be assigned to the on-treatment period. AEs will be distinguished for the treatment course in which the subjects are on-treatment as well as for screening, and post-study. The actual planned dosage of BI 836826 administered on the day each AE starts will also be derived and will be included in the listing. Listings of screening events will not be sorted by initial treatment. Post-study listings will be sorted by initial treatment.

According to the BI standards, multiple recordings of AEs will be collapsed to episodes on the lowest level term and multiple episodes will be condensed to records on the PT and SOC level. CTCAE grade will be an additional criterion for collapsing and condensing AEs. The maximum CTCAE grade will be assigned to episodes and records. CTCAE grade and DLT information will be displayed in AE listings. MedDRA levels for condensing will be SOC and PT.

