7.8.2 Laboratory data

The analyses of laboratory data will be descriptive in nature and will follow the standard procedure laid down in the DM & SM (Guideline 'Display and Analysis of Laboratory Data' [\(7\)](#)).

Patients will be counted under the initial treatment. The analysis of laboratory data will use the same ‘analysing treatments’ as described for the AEs, except for that the baseline laboratory value (as defined in [Section 6.7](#)) will be included in the ‘on-treatment’ period. Patients having at least one post-baseline laboratory value will be displayed in the descriptive analyses.

Single time courses by initial treatment will be used to display laboratory values over time. The graphs may be truncated if sufficient data is not available. These graphs will be displayed in Chapter 16.1.9.2 of the CTR for the following parameters, using the BI standardized values for haematology and differentials.

Haematology: haemoglobin, WBC count and platelets

Differentials: neutrophils (absolute count), absolute lymphocyte count, absolute Monocyte count and Natural Killer (NK) cells, CD 4 T-cell count

Biochemistry: LDH.

Clinically relevant abnormalities (as defined in [Section 9.2](#)) will also be summarised.

The change of the laboratory value will be calculated for all laboratory parameters from baseline to the end of the treatment for the whole treatment duration. No post-study laboratory values will be considered.

Worst laboratory value and its CTCAE grade (highest CTCAE grade) over all courses will be calculated for each laboratory parameter.

The change of the CTCAE grade of the lab value will be calculated

- from baseline to the last laboratory value on treatment
- from baseline to the worst value on treatment
- from worst value on treatment to last value on treatment

Note: For calculating the change in CTCAE grade from baseline, patients with a CTCAE grade of -9 (no CTCAE grade defined) will be treated as a CTCAE grade 0 for all analyses. In laboratory listings, the CTCAE grade is displayed as -9.

For Uric Acid and Hypokalemia, the CTCAE grade cannot always be assigned by the laboratory parameter itself as two different CTCAE grades have the same laboratory constellation, but are distinguished by additional clinical parameter. In this case a CTCAE grade of -1 will be assigned initially. Patients with a CTCAE grade of -1 will be treated as

- Grade 1 for Uric Acid
- Grade 1 for Hypokalemia

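### After 12 on-schedule infusions the course 3 footnote permits an EOT visit up to day 82, past the 8-week limit (day 78), and no visible SAP rule keeps a day 79-82 EOT laboratory sample on-treatment

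*Protocol*

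**What the plan says.** **Timing of the visit.** The EOT column of the protocol's Flowchart for Course 3 shows no day of its own and refers to footnote 12. For patients with 12 infusions the footnote states: "the EOT should be performed at the latest in week 26 (day 77±5 of course 3"). The legend under the same flowchart places the visit "at the latest 8 weeks after the last administration of BI 836826 (12 administrations"), and section 6.2.3.1 repeats the limit: "For patients who receive course 3 (12 administrations) at the latest 8 weeks after the last administration of BI 836826".

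**Assignment of laboratory values.** SAP 7.8.1.2 says that AEs from the first infusion "until 8 weeks after last administration of BI 836826 will be assigned to the on-treatment period". SAP 7.8.2 gives laboratory data the same periods "as described for the AEs, except for that the baseline laboratory value" joins the on-treatment period. It then states: "No post-study laboratory values will be considered". Just before that, it describes change from baseline as running to the end of treatment.

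**Boundary.** SAP 6.1 uses a strict less-than sign at the upper end: the "end date will determine whether the AE will be assigned to the" analysing treatment. The visible text does not define that end date.

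**Sampling.** Protocol 5.2.3.1 says of the direct antiglobulin test and immunoglobulins that they "have to be measured only at visit of first and last administration of each treatment course, at the EOT visit and during follow-up"; reticulocytes follow the same schedule. In the course 3 flowchart, as extracted, lymphocyte typing is marked at visit 8 and EOT but not at visit 9. The general safety laboratory is marked at every visit.

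**The concern.** A site that follows footnote 12 can hold the EOT visit on a day that the flowchart legend and section 6.2.3.1 do not allow. The SAP's on-treatment period ends at the 8-week point, so a scheduled safety sample taken under the footnote can fall just outside it and be treated as post-study.

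For most laboratory parameters this costs little, because visit 9 (day 71±5) supplies a nearby value. It costs more for parameters that are sampled rarely late in course 3. For immunoglobulins, direct antiglobulin test and reticulocytes, EOT is the only planned sample after day 22 that could count as on-treatment. For CD4+ T cells, which SAP 5.4.5.1 lists among the prioritized parameters for Section 15 of the report, the last remaining value would come from visit 8. Infections were the reason for the lower-dose Korean cohorts (protocol 2.2, SAP section 3), so late immune values are worth keeping.

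**Working it through.** **Inputs**
- Last infusion of course 3: day 22 (protocol 3.1 and the course 3 flowchart).
- Observation after it: 55 days (protocol 3.1).
- EOT window: day 77±5 (footnote 12).
- EOT cap: 8 weeks, or 56 days, after the last infusion (flowchart legend; section 6.2.3.1).
- End of the laboratory on-treatment period: 8 weeks after the last infusion (SAP 7.8.1.2 and 7.8.2).
- Visit 8: day 57±5. Visit 9: day 71±5 (course 3 flowchart).

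**The plan's own figure.** 22 + 55 = day 77, which reproduces the nominal day in footnote 12. The window is 77 − 5 = 72 to 77 + 5 = 82, or 11 days.

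**The cap.** 22 + 56 = day 78. The footnote therefore runs 82 − 78 = 4 days past it. Day 82 is 82 − 22 = 60 days after the last infusion, and 60/7 = 8.6 weeks. Days 79-82 are 4 of the 11 calendar days in the window.

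**The boundary day.** If the undefined end date in SAP 6.1 is day 78, the strict inequality also removes day 78, making 5 of 11 days. If it is day 79, the count stays at 4.

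**How far back the last on-treatment value moves for an EOT on days 79-82**

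| Parameter | Previous planned value | Move back, nominal day | With that visit's ±5 window |
|---|---|---|---|
| Immunoglobulins, direct antiglobulin test, reticulocytes | day 22 | 79 − 22 = 57 to 82 − 22 = 60 days | no window applied |
| Lymphocyte subsets, including CD4+ | visit 8, day 57 | 79 − 57 = 22 to 82 − 57 = 25 days | 79 − 62 = 17 to 82 − 52 = 30 days |
| Routine laboratory values | visit 9, day 71 | 79 − 71 = 8 to 82 − 71 = 11 days | 79 − 76 = 3 to 82 − 66 = 16 days |

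**A late twelfth infusion.** If it is k days late and the EOT date is not moved, the cap becomes day 78 + k and the affected days number max(0, 4 − k): 3, 2, 1 and 0 for k = 1, 2, 3 and 4. Protocol 6.1 allows administrative delays of 1-2 days and recalculates only the later treatment visits.

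**Which summaries lose the sample.** SAP 7.8.2 restricts the grade shifts to the last and worst values to on-treatment data, so a post-study EOT sample is out. SAP 5.4.5.1 says that immunoglobulins and the direct antiglobulin test have no CTCAE grade. For them the loss lies in worst-value and reference-range displays, and possibly in change from baseline.

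**The case against.** **The limits can be read together.** Day 77 is the nominal day, ±5 is an ordinary visit tolerance, and the cap stands on the same flowchart, so a careful site could apply both. That is possible. But the EOT column sends the site to the footnote and no order of precedence is given, so an EOT on days 79-82 is a foreseeable result of following the protocol.

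**The SAP may keep the sample after all.** Section 7.8.2 takes change from baseline to the end of treatment, and the EOT visit bears that name. A reader might infer that all three laboratory summaries lose the sample. The text does not support this for change from baseline: it can be read either way, because the next sentence bars post-study values. The last-value and worst-value summaries carry no such ambiguity.

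**Unseen documents may settle it.** SAP 6.1 refers period labels and coding to an ADS Plan, and 7.8.2 follows a sponsor guideline on laboratory data. Either may define the end date or place the EOT sample. This stands, so the claim is limited to the visible rules.

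**An 8-week limit is deliberate.** Protocol 7.3.3 and SAP 7.8.1.2 use it, and aligning laboratory data with AEs is reasonable. Moving the EOT sample creates a small inconsistency with the AE period. That is a genuine cost of the fix.

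**The week label.** A reader might infer that footnote 12 also misnames the week, since day 77 is the last day of week 25. The footnote gives week 26 as the latest time, and the upper end of the window, days 78-82, is in week 26. The label is not an error.

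**Conclusion.** The mismatch is real and minor. With the twelfth infusion on day 22, footnote 12 permits EOT 1 to 4 days beyond the 8-week cap. Under the visible SAP rules, a laboratory sample from those days is not counted in the on-treatment last-value and worst-value summaries. For change from baseline the plan is unclear.

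The size is per completer, because the documents do not give the number of patients with 12 infusions. A reader might take 4 of 11 (36%), or 5 of 11 (45%) if day 78 is also lost, as the share of completers affected. These are shares of calendar days in the window; the documents say nothing about how visits spread over it. The CD4+ consequence also rests on one blank cell in an extracted table.

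A reader might also infer that a safety conclusion is at risk. The documents do not support that. The tables are descriptive, the sample is still collected, and a clinically relevant abnormality can be recorded as an AE (protocol 5.2.2.1). The MTD evaluation period ends 7 days after the second infusion, so MTD and its DLT count cannot be affected, and no efficacy endpoint uses these values. The low-count episode analyses in SAP 7.8.2 have their own EOT rules and are outside this point. If infusion 12 is 4 or more days late and EOT is not moved, the gap beyond the cap disappears.

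**What to change.** **SAP 7.8.2, one sentence:** for patients who received 12 infusions, the laboratory sample from the EOT visit counts as on-treatment whatever its day. This keeps the sample in the last-value and worst-value summaries and removes the doubt over change from baseline. It needs no extra visit or sample. The downside is a mismatch of up to 4 days within the footnote window: a day 82 laboratory value would be on-treatment while an AE starting that day would be post-study. A table footnote can say so.

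**SAP 6.1, one clause, as a clarification only:** define the end date as the day after the 8-week point, so that day 78 is included, unless the ADS Plan already does this.

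**Protocol, secondary:** set footnote 12 to day 77 (−5/+1), which is days 72 to 78 and respects the cap for a patient on schedule. Protocol 8.1 requires ethics and authority approval for amendments, so this should wait for one made for other reasons.

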## **ABBREVIATIONS**

ADCC	Antibody dependent cellular cytotoxicity
AE	Adverse event
ALT	Alanine amino transferase
anti-HBs	Hepatitis B surface antibody
anti-HBc	Hepatitis B core antibody
anti-HCV	Hepatitis C antibody
AP	Alkaline phosphatase
aPTT	Activated partial thromboplastin time
AST	Aspartate amino transferase
B-NHL	B cell Non-Hodgkin lymphoma
CD	Cluster of Differentiation
CDC	Complement dependent cytotoxicity
CHOP	cyclophosphamide, hydroxydaunorubicin, oncovin , and prednisolone
CI	Confidence Interval

**Proprietary confidential information.**

**© 2016 Boehringer Ingelheim International GmbH or one or more of its affiliated companies. All rights reserved.**

This document may not - in full or in part - be passed on, reproduced, published or otherwise used without prior written permission.

CLL	Chronic lymphocytic leukaemia
CMV	Cytomegalovirus
CNS	Central nervous system
COPD	Chronic Obstructive Pulmonary Disease
CR	Complete remission
CRA	Clinical Research Associate
CRF	Case Report Form
CRO	Clinical Research Organisation
CRu	Complete remission unconfirmed
CT	Computer tomography
CTCAE	Common Terminology Criteria for Adverse Events
CTMF	Clinical Trial Master File
CTP	Clinical Trial Protocol
CTR	Clinical Trial Report
DILI	Drug-Induced Liver Injury
DLBCL	Diffuse large B-cell lymphoma
DLT	Dose limiting toxicity
DNA	Deoxyribonucleic acid
DSMB	Data Safety Monitoring Board
eCRF	Electronic Case Report Form
ECG	Electrocardiogram
ECOG	Eastern Cooperative Oncology Group

**Proprietary confidential information.**

**© 2016 Boehringer Ingelheim International GmbH or one or more of its affiliated companies. All rights reserved.**

This document may not - in full or in part - be passed on, reproduced, published or otherwise used without prior written permission.

EOT	End of treatment
EudraCT	European Clinical Trials Database
FAS	Full Analysis Set
FDA	Food and Drug Administration
FFS	Failure free survival
FL	Follicular lymphoma
FU	Follow-up
GCP	Good Clinical Practice
G-CSF	Granulocyte colony stimulating factor
GFR	Glomerular filtration rate
GvHD	Graft versus host disease
HBsAg	Hepatitis B surface antigen
HBV	Hepatitis B Virus
HCV	Hepatitis C Virus
HIV	Human immunodeficiency virus
IB	Investigator's Brochure
ICH	International Conference on Harmonization
IEC	Independent Ethics Committee
INR	International normalised ratio
IPI	International prognostic index
IRB	Institutional Review Board

